Free T4 and TSH	C1: D1, 22; C2 and beyond: D1	Pre-Infusion	-3 to 0 days prior to dosing
Prothrombin time; Activated partial thromboplastin time	C1: D1; C2 and beyond: D1	Pre-Infusion	-3 to 0 days prior to dosing
Urinalysis	C1: D1, 22; C2 and beyond: D1, 22	Pre-Infusion	-3 to 0 days prior to dosing
Study Drug Infusion Duration	C1: D1, 22, C2 and beyond: D1, 22, 43	NA	+10 min

Abbreviations: ADA= Anti-drug antibodies; C=cycle; D=day; min=minutes; EOI=end of infusion; NA=not applicable; SOI=start of infusion;

Appendix 2 Pharmacokinetics, Immunogenicity, and Pharmacodynamic Biomarkers Blood Sampling Schedule for MGA271+MGA012 (Cohort 4 Only)

Tumor Assessment Cycle	Day	Time Points	PK MGA271 And MGA012	ADA MGA271 and MGA012	Cytokines	Flow Cytometry Occupancy	Flow Cytometry Subsets	Soluble B7-H3 and Other Soluble Proteins
Cycle 1 and 2	1	Pre MGA012	x	x	x	x	x	x
		EOI MGA012	x					
		EOI MGA271	x					
	1	5 hr. after start of MGA271 infusion	x		x	x	x	
	2	No specific time point	x		x	x	x	
	4	No specific time point	x					
	8	No specific time point	x			x		x
	15	No specific time point	x			x	x	
	22	Pre MGA012	x	x		x	x	x
	22	EOI MGA012	x					
	22	EOI MGA271	x			x		
Cycle 3 and Beyond	1	Pre MGA012	x	x		x	x	
		EOI MGA012	x					
		EOI MGA271	x			x		
	22	Pre MGA012	x	x		x	x	
		EOI MGA012	x					
		EOI MGA271	x			x		
IRR/CRS		No specific time point			x			
EOTV		No specific time point	x	x			x	x

- Actual start and end of infusion times and PK sample collection times will be recorded on the CRFs.
- All Pre-dose samples will be collected prior to MGA012 infusion. ADA samples will be collected simultaneously with pre-infusion PK samples.
- Flow cytometry samples (occupancy and subset) will be collected through Cycle 4.

- Cytokine samples will be performed according to the table above. Additional samples should be obtained selectively at additional time points in patients who experience signs and symptoms of cytokine release at the time of the adverse event, with the goal to obtain a cytokine sample immediately at the time of onset of adverse event; specific dates and times of blood draws must be recorded.

Abbreviations: ADA= Anti-drug antibodies; C=cycle; D=day; min=minutes; EOI=end of infusion; NA=not applicable; SOI=start of infusion;

In Editing

Appendix 3 Definition of PFS

Situation	Date	Outcome
No baseline tumor assessments	Date of 1 st dose	Censored
Death prior to the 1 st scheduled tumor assessment	Date of death	Progressed
No post-baseline tumor assessments in absence of death prior to the 1 st scheduled tumor assessment	Date of 1 st dose	Censored
Documented disease progression	Date of disease progression	Progressed
Initiation of alternative anti-cancer treatments in absence of PD	Date of last tumor assessment prior to initiation of such treatment	Censored
Death or progression immediately after missing two or more consecutive scheduled tumor assessments	Date of last tumor assessment prior to missed assessments	Censored

**Appendix 4 Eastern Cooperative Oncology Group (ECOG)
Performance Status**

Grade	Description
0	Fully active, able to carry on all pre-disease performance without restriction.
1	Restricted in physically strenuous activity, but ambulatory and able to carry out work of a light or sedentary nature (e.g., light house work or office work)
2	Ambulatory and capable of all self-care, but unable to carry out any work activities. Up and about more than 50% of waking hours.
3	Capable of only limited self-care, confined to bed or chair more than 50% of waking hours.
4	Completely disabled. Cannot carry-on any self-care. Totally confined to bed or chair.
5	Dead

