PFS will be calculated as the time from the first dose of study drug until documented disease progression or death from any cause, whichever occurs first ([Appendix 3](#)). A patient's PFS will be censored if at the time of last assessment for progression, the patient remains progression free. PFS will be determined using both conventional RECIST 1.1 and immune-related response criteria.

Overall survival (OS)

OS will be calculated as the time from the first dose of study drug until death due to any cause or last observation or contact, whichever occurs first. A patient's OS will be censored if at the time of last contact, the patient remains alive. In addition, landmark 6-month OS rate will be determined.

Pharmacokinetic Assessments:

Serum concentrations of MGA271 and MGA012 will be monitored using a quantitative sandwich enzyme-linked immunosorbent assays (ELISA). Single and multiple dose PK parameters for MGA271 and MGA012, C_{max} , T_{max} , AUC_{tau} , C_{trough} , CL, V_{ss} , and $t_{1/2}$ will be derived from MGA271 and MGA012 serum concentration versus time data. Population PK analyses may be conducted using data from this study alone or combined with data from other studies.

Immunogenicity Assessments:

The generation of anti-drug antibodies (ADA) directed against MGA271 and MGA012 will be assayed using ELISA or Electrochemiluminescence method.

Pharmacodynamics/Biomarkers:

Tests Performed for both Dose Escalation and Cohort Expansion Patients:

- Characterization of alterations in serum cytokine levels including, but not limited to, IL-2, IL-6, IL-10, and TNF- α
- Enumeration of lymphocyte subsets, NK cells and activation status over time via multi-parameter flow cytometry on whole blood; evaluation of the regulatory T cell population over time
- Determination of B7-H3 and PD-L1 expression as well as immune cell infiltration into the tumor (e.g. CD8+ and CD4+ T cell infiltration) will be explored via IHC staining or other method of archival tumor biopsy specimens (unless fresh tumor sample submitted and used to determine B7-H3 expression and no archived sample obtained)
- Soluble B7-H3 over time analyzed by ELISA; in addition to other potential circulating serum biomarkers indicative of potential tumor response

Testing
Tests Performed for Cohort Expansion Patients:

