9.5 Efficacy Endpoints

Response will be categorized as CR, PR, SD, or PD and evaluated using RECIST 1.1 criteria ([Appendix 5](#)) and as irCR, irPR, irSD, or irPD using the immune-related response criteria (i.e., irRECIST as defined in [Appendix 6](#)). The ORR will be the proportion of patients in the response evaluable population achieving CR or PR when such responses are confirmed at least 28 days after the initial observation of an objective response. A two-sided 95% exact binomial confidence interval will be calculated around the ORR for each expansion cohort.

Response duration will be calculated for responders as the time from initial response (CR or PR) to the time of PD or death, whichever occurs first. Kaplan-Meier methods will be used to estimate response duration over time and the median response duration. Responders who complete the study without documented PD will be censored at the date of their last tumor assessment.

PFS and irPFS will be calculated as the time from the initial infusion of pembrolizumab or MGA271 until documented disease progression, or death from any cause. Patients with no PFS event (disease progression or death from any cause) will be censored at the date of their last tumor assessment. In addition, PFS and irPFS rates will be calculated at 3-month and 6-

month time points from the first dose of study drug. Kaplan-Meier methods will be used to estimate PFS over time and the median duration of PFS. The method of Brookmeyer and Crowley (9) will be used to construct 95% CIs around PFS estimates of the median and other quartiles for each expansion cohort.

Incomplete and missing data can complicate interpretation of PFS. [Appendix 3](#) describes the handling of these data for the PFS analysis.

Overall survival is defined as the time from the initial infusion of pembrolizumab or MGA271 to death from any cause. Kaplan-Meier methods will be used to estimate the overall survival function. Patients who do not die will be censored at the date that the patient was last known to be alive. In addition, OS will be calculated at 6 months from the first dose of study drug.

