5 ENDPOINTS AND COVARIATES

5.1 Efficacy Endpoints

Response will be categorized as complete response (CR), partial response (PR), stable disease (SD), or progressive disease (PD) and evaluated using RECIST 1.1 criteria and as immune-related complete response (irCR), immune-related partial response (irPR), immune-related stable disease (irSD), or immune-related progressive disease (irPD) using irRC. The ORR will be the proportion of patients in the response evaluable population achieving CR or PR when such responses are confirmed at least 28 days after the initial observation of an objective response. A two-sided 95% exact binomial confidence interval will be calculated around the ORR for each expansion cohort.

Duration of response (DoR) will be calculated for responders as the time from initial response (CR or PR) to the time of PD or death, whichever occurs first. Kaplan-Meier methods will be used to estimate DoR over time and the median DoR. Responders who complete the study without documented PD will be censored at the date of their last tumor assessment.

PFS and irPFS will be calculated as the time from the initial infusion of pembrolizumab or MGA271 until documented disease progression, or death from any cause. Patients with no PFS event (disease progression or death from any cause) will be censored at the date of their last tumor assessment. In addition, PFS and irPFS rates will be calculated at 3-month and 6-month year time points from the first dose of study drug. Kaplan-Meier methods will be used to estimate PFS over time and the median duration of PFS. The method of Brookmeyer and Crowley (1) will be used to construct 95% CIs around PFS estimates of the median and other quartiles for each expansion cohort.

Incomplete and missing data can complicate interpretation of PFS. **Table 3** describes the handling of these data for the PFS analysis.

Overall survival (OS) is defined as the time from the initial infusion of pembrolizumab or MGA271 to death from any cause. Kaplan-Meier methods will be used to estimate the overall survival function. Patients who do not die will be censored at the date that the patient was last known to be alive. In addition, OS will be calculated at 6 months from the first dose of study drug.

Table 3 Censoring Rules for PFS Analysis

Situation	Date	Outcome
No baseline tumor assessments	Date of 1 st dose	Censored
Death prior to the 1 st scheduled tumor assessment	Date of death	Progressed

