No post-baseline tumor assessments in absence of death	Date of 1 st dose	Censored

Situation	Date	Outcome
prior to the 1 st scheduled tumor assessment		
Documented disease progression	Date of disease progression	Progressed
Initiation of alternative anti-cancer treatments in absence of disease progression	Date of last tumor assessment prior to initiation of such treatment	Censored
Death or disease progression immediately after missing two or more consecutive scheduled tumor assessments	Date of last tumor assessment prior to missed assessments	Censored

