6.6.3 Time-to-Event Analyses

Kaplan-Meier methods will be used to estimate cumulative probabilities and quartiles (25th percentile, median, and 75th percentile) of time-to-event endpoints (DoR, PFS, irPFS, and OS). The method of Brookmeyer and Crowley (1) will be used to construct two-sided 95% CIs around the quartile estimates. These calculations will be performed for all patients in cohort expansion by tumor type. Additional analysis may be carried out, by tumor type, on patients in the dose escalation cohort combined with those in the expansion cohort.

DoR will be calculated from the time of initial response (CR or PR) documentation (in patients who have a subsequent confirmation of objective response) to the time of progressive disease or death, whichever occurs first. Patients with CR or PR at time of last assessment will be censored at the time of their last tumor assessment. DoR will be calculated as follows:

DoR (months) = (progression date or death date or date of last tumor assessment – date of initial response+1) / (365.25/12)

PFS is defined as the time from first dose of study drug until documented disease progression or death from any cause, or date of last tumor assessment. A patient will be censored at the time of last assessment if the patient remains progression free at that time. Progression will be assessed using both RECIST 1.1 and irRC. PFS will be calculated as follows:

PFS (months) = (date of progression or date of death or date of last tumor assessment – date of first dose+1) / (365.25/12)

Overall survival (OS) is calculated from the time of first dose until death from any cause. Patients alive at study completion will be censored for analysis purposes. OS will be calculated as follows:

$$\text{OS (months)} = (\text{date of last contact or death date} - \text{date of first dose} + 1) / (365.25/12)$$

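### The PFS censoring tables drop, at first dose, a never-scanned patient who dies between the first (Day 42) and second (Day 105) scheduled scans, although the PFS text counts that death as an event

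*Protocol*

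**What the plan says.** Protocol Appendix 3 and SAP Table 3 carry the same six rows. Three matter here.

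- **Early death.** "Death prior to the 1 st scheduled tumor assessment": an event, dated at death.
- **No scan.** "No post-baseline tumor assessments in absence of death prior to the 1 st scheduled tumor assessment": censored at the date of first dose. In the SAP this row is split by a page break. Its first part reads "No post-baseline tumor assessments in absence of death" and the limit to the first scheduled assessment follows on the next page, so the SAP row is the same as the protocol's.
- **Missed scans.** "Death or disease progression immediately after missing two or more consecutive scheduled tumor assessments": censored at the last assessment before the missed ones.

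The text defines the event without such limits. The Protocol Synopsis runs PFS "until documented disease progression or death from any cause, whichever occurs first", and Protocol 9.5 runs it "until documented disease progression, or death from any cause". SAP 6.6.3 says "PFS is defined as the time from first dose of study drug until documented disease progression or death from any cause". SAP 5.1 says "Patients with no PFS event (disease progression or death from any cause) will be censored at the date of their last tumor assessment", and Protocol 9.5 has the same censoring sentence. Protocol 9.5 and SAP 5.1 then send incomplete and missing data to the table.

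PFS is analysed in the Safety Population (Protocol 9.2.1, SAP 4.1), so patients without any post-baseline scan are included.

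**The concern.** The no-scan row takes the Day 42 cut-off from the early-death row and not the two-missed-scans limit from the last row. That leaves a window in which a known death is neither an early death nor a death after two missed scans, and the no-scan row removes the patient at time zero.

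The case can arise. The End of Treatment visit, which carries a scan, is optional (Protocol 8.3). Symptomatic deterioration is not objective progression (Protocol Appendix 5). Survival is followed by telephone (Protocol 4.1.4), so a death can be known for a patient who was never rescanned.

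Censoring at first dose is plausibly informative: a patient who is never rescanned and dies early has probably done badly. Removing such patients tends to flatter early PFS and irPFS. At stake are a small bias in a descriptive estimate and an analysed endpoint that differs from the stated one in this window.

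**Working it through.** **Calendar.** The first scan is on Study Day 42 (Protocol 4.1.1, SAP 3.1.1). Later scans are on Day 63 of each 9-week cycle, so the second is at 42 + 63 = Study Day 105. Month 3 is 3 × 365.25/12 = 91.3 days.

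**Applying the rows to a never-scanned patient with no new therapy who dies on Day 60.**

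1. Early death: no, because Day 60 is after Day 42.
2. Missed scans: no, because only one scan has been missed.
3. No scan: yes. The patient is censored at first dose and contributes (0 + 1)/(365.25/12) = 0.03 months with no event.
4. Text of SAP 5.1 and 6.6.3: the same patient has an event at (59 + 1)/(365.25/12) = 1.97 months, taking Day 1 as first dose.

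**Effect on a rate.** If *k* such patients die by time *t* and nobody else is censored before *t*, the estimate at *t* is inflated by N/(N − k). For k = 1 this is 20/19 = 1.05 or 16/15 = 1.07.

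Illustration at Month 3 with 12 of 20 progression-free:

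- Death counted: 12/20 = 60.0% (exact 95% CI 36.1% to 80.9%).
- One death by Month 3 censored at first dose: 12/19 = 63.2%, a shift of 3.2 points.
- One death in Days 92-105 censored at first dose: the patient was still among the 12 at Month 3, so the rate falls to 11/19 = 57.9%. By Month 6 all these deaths act in the favourable direction.

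**Frequency.** Exponential survival is assumed, S(t) = 2^(−t/median). The median is 178 days for the 40 SCCHN patients, the background figure in Protocol 2.1. It is 365.25 days for the other 72 expansion patients, an assumption.

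| | 178 d | 365.25 d | Deaths in 112 patients |
|---|---|---|---|
| Day 42 to Month 3 | 0.1483 | 0.0825 | 40 × 0.1483 + 72 × 0.0825 = 11.87 |
| Day 42 to Day 105 | 0.1847 | 0.1041 | 40 × 0.1847 + 72 × 0.1041 = 14.88 |

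Suppose 10-30% of these had no post-baseline scan; the documents give no figure.

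- By Month 3: 1.2 to 3.6 of 112. Per cohort, from 16 × 0.0825 × 0.1 = 0.13 to 20 × 0.1483 × 0.3 = 0.89.
- Whole window: 1.5 to 4.5 of 112. Per cohort, from 16 × 0.1041 × 0.1 = 0.17 to 20 × 0.1847 × 0.3 = 1.11, the upper end being SCCHN only.

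**The case against.** **The text fills the gap.** The tables state no order of precedence and have no general death row. A patient scanned on Day 42 who dies on Day 60 without progression is an event only through the text. On this argument the text should govern the never-scanned patient too, and the row is merely awkward. The premise is right, and it disposes of one tempting inference: that the table contradicts itself by treating two patients with one missed scan differently. The patient who was scanned on Day 42, missed Day 105 and then died is an event by the text and by no row. The conflict is therefore between table and text. But the conclusion does not follow. A gap can be filled from the text; a row that expressly covers the never-scanned patient, and names the one death it excepts, is not a gap.

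**The plan means to censor some deaths.** Appendix 3 is offered as the definition of PFS, and the missed-scan row censors deaths openly. This stands. A reader might infer that every censored death breaches the stated endpoint, and the documents do not support that. Censoring after two or more missed scans is a deliberate choice, and nothing here disturbs it.

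**The size rests on assumptions.** This also stands. The no-scan share is not in the documents. End of Treatment scans and the instruction in Protocol Appendix 5 to keep trying to document progression after discontinuation may lower it. ECOG 0-1 and a life expectancy of at least 12 weeks make 178 days a pessimistic median. Patients who withdraw before the first scan for reasons other than progression may be replaced (Protocol 4.7.1), which may keep the number at risk near 20. Deaths after withdrawal of consent may not be known.

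**Conclusion.** The point holds for one window. Read as written, both tables censor at first dose a never-scanned patient who dies on or after Day 42 and before Day 105 without new therapy. The text counts that death, and no reason is given for excluding it.

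The effect is minor. On the assumed shares, fewer than one patient per cohort is affected by Month 3, and about one at most over the whole window. One such death by Month 3 shifts the illustrative rate by 3.2 points, against an exact interval about 45 points wide. A reader might infer that the reported PFS is materially biased. The documents do not support this: PFS is secondary and descriptive, no test or decision rule rests on it, and deaths in Days 92-105 move the 3-month rate the other way.

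**What to change.** In both tables:

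1. Leave the row for death before the first scheduled assessment unchanged. Adding a no-new-therapy condition there would turn deaths that now count as events into censorings at first dose, which moves away from the stated endpoint and in the favourable direction.
2. Add a row: *Death on or after the 1st and before the 2nd scheduled tumor assessment, with no post-baseline assessment and no alternative anti-cancer therapy started: date of death, event.*
3. Change the no-scan row to: *No post-baseline tumor assessment and no death counted as an event in the rows above: date of 1st dose, censored.*
4. State that for never-scanned patients the no-scan row sets the censoring date, ahead of the missed-scan and new-therapy rows. Otherwise the last assessment could be the pre-dose baseline scan. At the four-week limit in Protocol Appendix 5, the SAP 6.6.3 formula would give (−28 + 1)/(365.25/12) = −0.89 months.

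The cost is an SAP edit and a matching amendment to Protocol Appendix 3, with sponsor approval and IRB/IEC approval when required (Protocol 11.1). No new data are needed. Early PFS may become slightly less favourable. Pembrolizumab-cohort results have already been presented (Protocol 2.3.1.1.2), so the change should be dated and labelled as made after that.

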Appendix 5 RECIST 1.1 Guidelines

(Adapted from Eisenhauer 2009 (19))

All patients will be required to have at least 1 measurable lesion to be considered as having measurable disease at baseline for the determination of eligibility for this study. Measurable lesions are defined below.

MEASURABILITY OF TUMOR AT BASELINE

DEFINITIONS

At baseline, tumor lesions/lymph nodes will be categorized measurable or non-measurable as follows:

Measurable

Tumor lesions: Must be accurately measured in at least one dimension (*longest diameter* in the plane of measurement is to be recorded) with a *minimum* size of:

- 10 mm by CT scan (CT scan slice thickness no greater than 5 mm).
- 10 mm caliper measurement by clinical exam (lesions which cannot be accurately measured with calipers should be recorded as non-measurable).
- 20 mm by chest X-ray.

Malignant lymph nodes: To be considered pathologically enlarged and measurable, a lymph node must be ≥ 15 mm in *short axis* when assessed by CT scan (CT scan slice thickness recommended to be no greater than 5 mm). At baseline and in follow-up, only the *short axis* will be measured and followed. See also notes below on 'Baseline documentation of target and non-target lesions' for information on lymph node measurement.

Non-measurable

All other lesions, including small lesions (longest diameter < 10 mm or pathological lymph nodes with ≥ 10 to < 15 mm short axis) as well as truly non-measurable lesions. Lesions considered truly non-measurable include: leptomeningeal disease, ascites, pleural or pericardial effusion, inflammatory breast disease, lymphangitic involvement of skin or lung, abdominal masses/abdominal organomegaly identified by physical exam that is not measurable by reproducible imaging techniques.

Special considerations regarding lesion measurability

Bone lesions, cystic lesions, and lesions previously treated with local therapy require particular comment:

Bone lesions:

- Bone scan, PET scan or plain films are not considered adequate imaging techniques to measure bone lesions. However, these techniques can be used to confirm the presence or disappearance of bone lesions.
- Lytic bone lesions or mixed lytic-blastic lesions, with identifiable soft tissue components, that can be evaluated by cross sectional imaging techniques such as CT or MRI can be considered as measurable lesions if the soft tissue component meets the definition of measurability described above.
- Blastic bone lesions are non-measurable.

Cystic lesions:

- Lesions that meet the criteria for radiographically defined simple cysts should not be considered as malignant lesions (neither measurable nor non-measurable) since they are, by definition, simple cysts.
- ‘Cystic lesions’ thought to represent cystic metastases can be considered as measurable lesions, if they meet the definition of measurability described above. However, if non-cystic lesions are present in the same patient, these are preferred for selection as target lesions.

Lesions with prior local treatment:

- Tumor lesions situated in a previously irradiated area, or in an area subjected to other loco-regional therapy, are not considered measurable unless there has been demonstrated progression in the lesion prior to study enrollment.

SPECIFICATIONS BY METHODS OF MEASUREMENTS**Measurement of lesions**

All measurements should be recorded in metric notation, using calipers if clinically assessed. All baseline evaluations should be performed as close as possible to the treatment start and never more than 4 weeks before the beginning of the treatment.

Method of assessment

The same method of assessment and the same technique should be used to characterize each identified and reported lesion at baseline and during follow-up. Imaging based evaluation should always be done rather than clinical examination unless the lesions(s) being followed cannot be imaged but are assessable by clinical exam.

Clinical lesions: Clinical lesions will only be considered measurable when they are superficial and ≥ 10 mm diameter as assessed using calipers (e.g. skin nodules). For the case of skin lesions, documentation by color photography including a ruler to estimate the size of the lesion is suggested. As noted above, when lesions can be evaluated by both clinical exam and imaging, imaging evaluation should be undertaken since it is more objective and may also be reviewed at the end of the study.

Chest X-ray: Chest CT is preferred over chest X-ray, particularly when progression is an important endpoint, since CT is more sensitive than X-ray, particularly in identifying new lesions. However, lesions on chest X-ray may be considered measurable if they are clearly defined and surrounded by aerated lung.

CT, MRI: CT is the best currently available and reproducible method to measure lesions selected for response assessment. This guideline has defined measurability of lesions on CT scan based on the assumption that CT slice thickness is 5 mm or less. When CT scans have slice thickness greater than 5 mm, the minimum size for a measurable lesion should be twice the slice thickness. MRI is also acceptable in certain situations (e.g. for body scans).

Ultrasound: Ultrasound is not useful in assessment of lesion size and should not be used as a method of measurement. Ultrasound examinations cannot be reproduced in their entirety for independent review at a later date and, because they are operator dependent, it cannot be guaranteed that the same technique and measurements will be taken from one assessment to the next. If new lesions are identified by ultrasound in the course of the study, confirmation by CT or MRI is advised. If there is concern about radiation exposure at CT, MRI may be used instead of CT in selected instances.

Endoscopy, laparoscopy: The utilization of these techniques for objective tumor evaluation is not advised.

Tumor markers: Tumor markers *alone* cannot be used to assess *objective* tumor response.

TUMOR RESPONSE EVALUATION

ASSESSMENT OF OVERALL TUMOR BURDEN AND MEASURABLE DISEASE

To assess objective response or future progression, it is necessary to estimate the *overall tumor burden at baseline* and use this as a comparator for subsequent measurements. Only patients with measurable disease at baseline should be included. Measurable disease is defined by the presence of at least one measurable lesion (as detailed above).

BASELINE DOCUMENTATION OF 'TARGET' AND 'NON-TARGET' LESIONS

Where more than one measurable lesion is present at baseline all lesions up to a maximum of five lesions total (and a maximum of two lesions per organ) representative of all involved

organs should be identified as *target lesions* and will be recorded and measured at baseline. For example, in instances where patients have only one or two organ sites involved, a maximum of two and four lesions respectively will be recorded). Target lesions should be selected on the basis of their size (lesions with the longest diameter), be representative of all involved organs, but in addition should be those that lend themselves to *reproducible repeated measurements*. It may be the case that, on occasion, the largest lesion does not lend itself to reproducible measurement in which circumstance the next largest lesions which can be measured reproducibly should be selected.

Lymph nodes merit special mention since they are normal anatomical structures which may be visible by imaging even if not involved by tumor. As noted above, pathological nodes which are defined as measurable and may be identified as target lesions must meet criterion of a short axis of ≥ 15 mm by CT scan. Only the *short axis* of these nodes will contribute to the baseline sum. The short axis of the node is the diameter normally used by radiologists to judge if a node is involved by solid tumor. Nodal size is normally reported as two dimensions in the plane in which the image is obtained (for CT scan this is almost always the axial plane; for MRI the plane of acquisition may be axial, sagittal or coronal). The smaller of these measures is the short axis. For example, an abdominal node which is reported as being 20 mm x 30 mm has a short axis of 20 mm and qualifies as a malignant, measurable node. In this example, 20 mm should be recorded as the node measurement. All other pathological nodes (those with short axis ≥ 10 mm but < 15 mm) should be considered non-target lesions. Nodes that have a short axis < 10 mm are considered non-pathological and should not be recorded or followed.

A *sum of the diameters* (longest for non-nodal lesions, short axis for nodal lesions) for all target lesions will be calculated and reported as the *baseline sum diameters*. If lymph nodes are to be included in the sum, then as noted above, only the *short axis* is added into the sum. The baseline sum diameters will be used as reference to further characterize any objective tumor regression in the measurable dimension of the disease.

All other lesions (or sites of disease) including pathological lymph nodes should be identified as *non-target lesions* and should also be recorded at baseline. Measurements are not required and these lesions should be followed as 'present', 'absent', or in rare cases 'unequivocal progression. In addition, it is possible to record multiple non-target lesions involving the same organ as a single item on the case record form (e.g. 'multiple enlarged pelvic lymph nodes' or 'multiple liver metastases').

RESPONSE CRITERIA

This section provides the definitions of the criteria used to determine objective tumor response for target lesions.

Evaluation of target lesions

Complete Response (CR): Disappearance of all target lesions. Any pathological lymph nodes (whether target or non-target) must have reduction in short axis to < 10 mm.

Partial Response (PR): at least a 30% decrease in the sum of diameters of target lesions, taking as reference the baseline sum diameters.

Progressive Disease (PD): at least a 20% increase in the sum of diameters of target lesions, taking as reference the *smallest sum on study* (this includes the baseline sum if that is the smallest on study). In addition to the relative increase of 20%, the sum must also demonstrate an absolute increase of at least 5 mm. (*Note*: the appearance of one or more new lesions is also considered progression).

Stable Disease (SD): Neither sufficient shrinkage to qualify for PR nor sufficient increase to qualify for PD, taking as reference the smallest sum diameters while on study.

Special notes on the assessment of target lesions

Lymph nodes. Lymph nodes identified as target lesions should always have the actual short axis measurement recorded (measured in the same anatomical plane as the baseline examination), even if the nodes regress to below 10 mm on study. This means that when lymph nodes are included as target lesions, the ‘sum’ of lesions may not be zero even if complete response criteria are met, since a normal lymph node is defined as having a short axis of <10 mm. In order to qualify for CR, each node must achieve a short axis <10 mm. For PR, SD and PD, the actual short axis measurement of the nodes is to be included in the sum of target lesions.

Target lesions that become ‘too small to measure’. While on study, all lesions (nodal and non-nodal) recorded at baseline should have their actual measurements recorded at each subsequent evaluation, even when very small (e.g. 2 mm). However, sometimes lesions or lymph nodes which are recorded as target lesions at baseline become so faint on CT scan that the radiologist may not feel comfortable assigning an exact measure and may report them as being ‘too small to measure’. When this occurs it is important that a value be recorded on the case report form. If it is the opinion of the radiologist that the lesion has likely disappeared, the measurement should be recorded as 0 mm. If the lesion is believed to be present and is faintly seen but too small to measure, a default value of 5 mm should be assigned (*Note*: It is less likely that this rule will be used for lymph nodes since they usually have a definable size when normal and are frequently surrounded by fat such as in the retroperitoneum; however, if a lymph node is believed to be present and is faintly seen but too small to measure, a default value of 5 mm should be assigned in this circumstance as well). This default value is derived from the 5 mm CT slice thickness (but should not be changed with varying CT slice thickness). The measurement of these lesions is potentially non-reproducible, therefore providing this default value will prevent false responses or progressions based upon measurement error. However, if the radiologist is able to provide an actual measure, that should be recorded, even if it is below 5 mm.

Lesions that split or coalesce on treatment. When non-nodal lesions ‘fragment’, the longest diameters of the fragmented portions should be added together to calculate the target lesion sum. Similarly, as lesions coalesce, a plane between them may be maintained that would aid in obtaining maximal diameter measurements of each individual lesions. If the lesions have

truly coalesced such that they are no longer separable, the vector of the longest diameter in this instance should be the maximal longest diameter for the ‘coalesced lesion’.

Evaluation of non-target lesions

This section provides the definitions of the criteria used to determine the tumor response for the group of non-target lesions. While some non-target lesions may actually be measurable, they need not be measured and instead should be assessed only *qualitatively* at the time points specified in the protocol.

Complete Response (CR): Disappearance of all non-target lesions. All lymph nodes must be non-pathological in size (<10mm short axis).

Non-CR/Non-PD: Persistence of one or more non-target lesions(s).

Progressive Disease (PD): Unequivocal progression (see comments below) of existing non-target lesions. (Note: the appearance of one or more new lesions is also considered progression).

Special notes on assessment of progression of non-target disease

The concept of progression of non-target disease requires additional explanation as follows:

When a patient also has measurable disease. In this setting, to achieve ‘unequivocal progression; on the basis of the non-target disease, there must be an overall level of substantial worsening in non-target disease such that, even in presence of SD or PR in target disease, the overall tumor burden has increased sufficiently to merit discontinuation of therapy. A modest ‘increase’ in the size of one or more non-target lesions is usually not sufficient to qualify for unequivocal progression status. The designation of overall progression *solely* on the basis of change in non-target disease in the face of SD or PR of target disease will therefore be extremely rare.

When the patient has only non-measurable disease. The same general concepts apply here as noted above, *however*, in this instance there is no measurable disease assessment to factor into the interpretation of an increase in non-measurable disease burden. Because worsening in non-target disease cannot be easily quantified (by definition: if all lesions are truly non-measurable) a useful test that can be applied when assessing patients for unequivocal progression is to consider if the increase in overall disease burden based on the change in non-measurable disease is comparable in magnitude to the increase that would be required to declare PD for measurable disease: i.e. an increase in tumor burden representing an additional 73% increase in ‘volume’ (which is equivalent to a 20% increase diameter in a measurable lesion). Examples include an increase in a pleural effusion from ‘trace’ to ‘large’, an increase in lymphangitic disease from localized to widespread, or may be described in protocols as ‘sufficient to require a change in therapy’. If ‘unequivocal progression’ is seen, the patient should be considered to have had overall PD at that point. While it would be ideal to have objective criteria to apply to non-measurable disease, the very nature of that disease makes it impossible to do so; therefore, the increase must be substantial.

New Lesions

The appearance of new malignant lesions denotes disease progression. There are no specific criteria for the identification of new radiographic lesions; however, the finding of a new lesion should be unequivocal: i.e. not attributable to differences in scanning technique, change in imaging modality or findings thought to represent something other than tumor (for example, some 'new' bone lesions may be simply healing or flare of pre-existing lesions). This is particularly important when the patient's baseline lesions show partial or complete response. For example, necrosis of a liver lesion may be reported on a CT scan report as a 'new' cystic lesion, which it is not.

A lesion identified on a follow-up study in an anatomical location that was *not* scanned at baseline is considered a new lesion and will indicate disease progression. An example of this is the patient who has visceral disease at baseline and while on study has a CT or MRI brain ordered which reveals metastases. The patient's brain metastases are considered to be evidence of PD even if he/she did not have brain imaging at baseline.

